9.3 SCREENING

Within the 28 days preceding first dose, all subjects will be required to undergo a screening visit. Screening procedures will be carried out in accordance with the schedule of assessments in Section 3.2 (SoA).

If the start of the study is delayed for any reason so that the interval between screening and first dose exceeds 28 days, all or part of the screening procedures will be repeated at the discretion of the investigator.

Screening safety procedures such as safety bloods, ECGs, vital signs, urine alcohol, urine cotinine, urine drug screen and urinalysis can be repeated as clinically indicated under the discretion of the investigator or sub-investigator if there is a concern regarding a subject's safety or eligibility to participate in the trial.

9.3.1 RE-SCREENING

This study permits the re-screening of a subject who has discontinued the study as a pre-treatment failure (i.e., subject has not been randomized); the reason for failure must be temporary and expected to resolve. If re-screened, the subject must be re-consented.

9.4 ADMISSION AND PRE-DOSE PROCEDURES

The identity of the subjects will be confirmed at admission and pre-dose.

In addition, the ongoing eligibility of subjects will be re-assessed at admission/pre-dose, as described in Sections 6.3 and 6.4.

Admission/pre-dose safety procedures such as safety bloods, ECGs, vital signs, urinalysis, and drugs of abuse tests can be repeated as clinically indicated under the discretion of investigator or sub-investigator if there is a concern regarding a subject's safety or eligibility to participate in the clinical trial.

Alternative subjects for the first dose occasion, in any group, will not require admission procedures to be repeated if dosing is within 2 days.

If dosing is delayed, subjects who have completed admission procedures do not need admission procedures to be repeated if dosing is within 2 days and the subjects have remained resident in the clinical unit.

The subjects will be admitted to the clinical unit in the morning on the day before dosing (Day -1).

The admission and pre-dose procedures are presented in Section 3.2 (SoA).

9.5 TIMING OF PROCEDURES

There are times where the protocol requires more than one procedure to be completed at the same time point. In these instances, the following will apply to post-dose time points:

- Sequencing: ECGs should be taken prior to vital signs when both measurements are scheduled at the same time point.
- Priority for precise timing: PK samples should take priority (i.e., taken at the nominal time point) over other procedures scheduled at the same time point
- Other assessments, e.g., physical examinations, will be performed within the required time windows.

As guidance, the preferred order of assessments is:

All safety assessments will be timed and performed relative to the start of dosing.

9.6 DISCHARGE FROM THE CLINICAL UNIT

Subjects will be discharged from the clinical unit following completion of study-specific procedures at 120 h post-dose (Day 6). However, the investigator may ask a subject to remain domiciled for additional safety observation and monitoring (e.g., as indicated for an AE).

9.7 FOLLOW-UP VISIT

Subjects will receive a follow-up call 7 days following dose administration to assess for any new AEs since discharge. A questionnaire will be followed for the follow-up interview.

9.8 DATA COLLECTION AND EVALUATION

All clinical raw data will be recorded promptly, accurately, and legibly; either directly into the e-source data or indelibly on paper (e.g., ECG readings). A detailed list of the type (electronic or paper) and location for all source data will be included in the Trial Master File. All raw data will be conserved in order to maintain data integrity. A physician and/or the clinical staff will assume the responsibility of ensuring the completeness and accuracy of the clinical data.

9.9 SUBJECT WITHDRAWAL AND REPLACEMENT

Subjects will be advised that they are free to withdraw from the study at any time. Over the course of the study, the Sponsor and the Investigator(s) or a delegate may withdraw any subject from the study for non-compliance with protocol requirements or significant protocol deviation. Subjects may also be withdrawn by the Investigator(s) or a delegate for:

- Pregnancy [if applicable]
- Termination of the study by the sponsor, regulatory agency, or IRB
- Upon the subject's request (withdrawal of consent)
- Significant deviation from the protocol
- Significant concurrent illness or requirement for prohibited medication
- Evidence of current SARS-CoV-2 infection
- Subject non-compliance
- At the discretion of the investigator

Clinical laboratory results will be reviewed by a Medical Sub-Investigator prior to dosing, when applicable; subjects will be withdrawn from the study if it is deemed that the subject's safety may be at risk on the basis of these test results.

Subjects who withdraw or are withdrawn from the study after dosing will not be systematically replaced. However, at least 7 (out of 8) subjects from a same dose level should have completed the dosing period, and safety and tolerability data collected up to the follow up visit should be available for these subjects before the SRC can decide on dose escalation. Therefore, subjects who withdraw or are withdrawn from the study after dosing for reasons other than safety and tolerability may be replaced after consultation between the Safety Committee members. In such case, the total number of subjects dosed will remain within a maximum of 10 subjects per cohort.

Subjects withdrawn for safety reasons will be asked to remain at the clinic until the Investigator(s) or a delegate agrees that the subject is fine and can be discharged. As soon as subject withdrawal is confirmed, blood sampling will be stopped.

The minimum number of evaluable subjects is 7 per cohort. An evaluable subject is defined as a subject who has pharmacokinetic, safety, and tolerability data out to 120 hours post dose, for evaluation of the primary objective.

9.10 ADVERSE EVENTS AND SERIOUS ADVERSE EVENTS

9.10.1 DEFINITION OF AN ADVERSE EVENT (AE)

An AE is any untoward medical occurrence in a subject who has been administered a pharmaceutical product or not, which does not necessarily have a causal relationship with this treatment. An AE can therefore be any unfavorable and unintended sign (including an abnormal laboratory finding judged clinically significant), symptom, or disease temporally associated with the use of a medicinal (investigational) product (study drug) or clinical procedure, whether or not it is related to the medicinal (investigational) product (study drug) or clinical procedure. An adverse drug reaction (ADR) is any AE where a causal relationship with the study drug is at least a reasonable possibility (possibly related or probably related).

9.10.2 DEFINITION OF A SERIOUS ADVERSE EVENT (SAE)

A SAE is any AE that at any dose:

- Results in death
- Is life-threatening (i.e., in the opinion of the principal investigator (PI) the subject is at immediate risk of death from the AE)
- Requires inpatient hospitalization or prolongation of existing hospitalization
- Results in persistent or significant disability/incapacity (a substantial disruption of the subject's ability to conduct normal life functions)
- Results in a congenital anomaly/birth defect
- Constitutes an important medical event:
 - These may not result in death, be life-threatening, or require hospitalization, but may be considered serious when they jeopardize the health of the subject and require medical or surgical intervention to prevent one of the outcomes listed.
 - Any other event (e.g., allergic bronchospasm requiring intensive treatment in an emergency room or at home, blood dyscrasias, convulsions that do not result in inpatient hospitalization, or the development of drug dependency or drug abuse) thought to be serious by the Principal Investigator

Version 2.0: 9 May 2022 Confidential Page 59

Events not considered to be serious are hospitalizations that:

- Were planned before entry into the clinical trial
- Are for elective treatment of a condition unrelated to the studied indication or its treatment
- Occur on an emergency outpatient basis and do not result in admission (unless fulfilling other criteria above)
- Are parts of the normal treatment or monitoring of the studied indication and are not associated with any deterioration in condition

9.10.3 DEFINITION OF SUSPECTED UNEXPECTED SERIOUS ADVERSE REACTIONS

Suspected Unexpected Serious Adverse ReactionS (SUSARs) are AEs that are believed to be related to a test product and are both unexpected (i.e., the nature or severity is not expected from the information provided in the IB) and serious. SUSARs are subject to expedited reporting to the IRB (see Section 9.10.8 for details on reporting SUSARs).

9.10.4 RECORDING OF ADVERSE EVENTS

AEs will be recorded and evaluated for their seriousness, severity, and relationship to the study treatment. AEs will be collected and documented from the time of providing written informed consent (screening) until 7 days after study drug administration. Subjects will be asked to self-report between day 8 (follow up call) and day 30 following drug administration. If emerging or ongoing AEs are reported at the follow-up phone call or after follow-up, additional visits and phone calls will be arranged as unscheduled visits. During each study visit the subject will be questioned directly regarding the occurrence of any adverse medical event according to the schedule in eCRF. All AEs, whether ascribed to study procedures or not, will be documented immediately in the subject's eCRF. AEs will be followed-up until complete resolution, or until the Investigator judges it safe to discontinue follow-up. The relationship to the study medication will be classified according to the categories described in Section 9.10.6. Classification of AEs will be performed by System Organ Class (SOC) and Preferred Term (PT) using the Medical Dictionary for Regulatory Activities (MedDRA), version 24.0 or higher.

Concomitant medications will be coded using the World Health Organization drug dictionary (WHO-DDE March 2021 or later).

9.10.5 ADVERSE EVENTS SEVERITY

The severity of AEs will be graded according to criteria from the NCI Common Terminology Criteria Adverse Events (CTCAE) version 5.0. (Table 6).

The CTCAE displays Grades 1 through 5 with unique clinical descriptions of severity for each AE based on this general guideline:

Table 6 NCI Common Terminology Criteria Adverse Events (CTCAE) version 5.0. Severity Grade

| GRADE | DESCRIPTION | | |
|---------|-------------------------------------------------------------------------------------------------------------------------------------------------------------------------------------------------------------------------------------------------------------------------------------------------------------------------------------------------------|--|--|
| Grade 1 | Mild; asymptomatic or mild symptoms; clinical or diagnostic observations only; intervention not indicated. | | |
| Grade 2 | Moderate; minimal, local or non-invasive intervention indicated; limiting ag appropriate instrumental activities of daily living (instrumental activities of daily living refer to preparing meals, shopping for groceries or clothes, using the telephone, managing money, etc.). | | |
| Grade 3 | Severe or medically significant but not immediately life-threatening; hospitalization or prolongation of hospitalization indicated; disabling; limiting self-care activities of daily living (self-care activities of daily living refer to bathing, dressing and undressing, feeding self, using the toilet, taking medications, and not bedridden). | | |
| Grade 4 | Life-threatening consequences; urgent intervention indicated. | | |
| Grade 5 | Death related to AE. *Grade 5 (death) is not appropriate for some AEs and therefore is not an option. | | |

AE = adverse event

9.10.6 ADVERSE EVENT CATEGORIES FOR DETERMINING RELATIONSHIP TO STUDY DRUG **PROBABLE** (first three conditions must apply)

This category applies to those AEs that are considered, with a high degree of certainty, to be related to the study drug. An AE may be considered probable, if:

- It follows a reasonable temporal sequence from administration of the drug.
- It cannot be reasonably explained by the known characteristics of the subject's clinical state, environmental, or toxic factors or other modes of therapy administered to the subject.
- It disappears or decreases on cessation or reduction of the dose. (There are important exceptions when an AE does not disappear upon discontinuation of the drug, yet drug relatedness clearly exists, e.g., (1) bone marrow depression, (2) tardive dyskinesias.)
- It follows a known pattern of response to the suspected drug.
- It reappears upon re-challenge.

POSSIBLE (first two conditions must apply)

This category applies to those AEs in which the connection with the study drug administration appears unlikely but cannot be ruled out with certainty. An AE may be considered possible if, or when:

- It follows a reasonable temporal sequence from administration of the drug.
- It may have been produced by the subject's clinical state, environmental or toxic factors or other modes of therapy administered to the subject.
- It follows a known pattern of response to the suspected drug.

REMOTE (first two conditions must apply)

In general, this category is applicable to an AE that meets the following criteria:

- It does not follow a reasonable temporal sequence from administration of the drug.
- It may readily have been produced by the subject's clinical state, environmental or toxic factors, or other modes of therapy administered to the subject.
- It does not follow a known pattern of response to the suspected drug.
- It does not reappear or worsen when the study drug is re-administered.

UNRELATED

This category is applicable to those AEs which are judged to be clearly and incontrovertibly due only to extraneous causes (disease, environment, etc.) and do not meet the criteria for study drug relationship listed under remote, possible, or probable.

Refer to Table 7 for determining relationship of AEs.

Page 63

Table 7 Determining the Relationship of Adverse Events to the Study Drug

| | Probable | Possible | Remote | Unrelated |
|---------------------------------------------------------------|----------|----------|--------|-----------|
| Clearly due to extraneous causes | _ | _ | _ | + |
| Reasonable temporal association with drug administration | | + | _ | _ |
| May be produced by subject clinical state, etc. | _ | + | + | + |
| Known response pattern to suspected drug | + | + | _ | _ |
| Disappears or decreases on cessation or reduction of the dose | + | _ | _ | _ |
| Reappears on re-challenge | + | _ | _ | _ |

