8.3.3 TRIAL STOPPING RULES

Dosing and/or recruitment will be interrupted until the SRC has completed a thorough review of all available data, for any of the following reasons, but not limited to:

• If 1 subject experiences an SAE

Clinical trial stopping rules:

- If 2 RVP-001 related SAEs occur in a cohort
- If 2 subjects experience severe RVP-001 related AEs
- Occurrence of an RVP-001 related AE or SAE which results in death

Relatedness to study drug will be determined by the investigator.

If the study is halted, the IRB will be notified. The study may be resumed or terminated; however, it will not be resumed until a further notice to resume the study is submitted and approved by the IRB.

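### The causality scale in Section 9.10.6 and Table 7 does not suit a single-bolus study and conflicts internally, so a temporally linked, unexplained, persistent AE can be left without a category that the stopping rules rely on.

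*Combined protocol and SAP*

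**What the plan says.** Section 9.10.4 sends every AE to the categories of Section 9.10.6 for its relationship to study drug.

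- **Probable** is headed "first three conditions must apply". The three are a reasonable temporal sequence; "It cannot be reasonably explained by the known characteristics of the subject's clinical state, environmental, or toxic factors" (or by other therapy); and "It disappears or decreases on cessation or reduction of the dose". The third bullet then adds an exception: "There are important exceptions when an AE does not disappear upon discontinuation of the drug, yet drug relatedness clearly exists", with two examples.
- **Possible** is headed "POSSIBLE (first two conditions must apply". The two are a temporal sequence and a possible alternative cause. The category is described as one where "the connection with the study drug administration appears unlikely but cannot be ruled out with certainty".
- **Remote** requires the absence of a temporal sequence and a ready alternative cause.
- **Unrelated** requires causes that are clearly and only extraneous.

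Table 7 shows dechallenge as a plus for Probable and a minus for the other three categories, with no exception. It also shows re-challenge as a plus for Probable, and a known response pattern as a plus for Probable and Possible.

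Section 9.10.1 defines an adverse drug reaction as an AE where "a causal relationship with the study drug is at least a reasonable possibility (possibly related or probably related". Sections 8.3.2 and 8.3.3 use relatedness in several stopping rules, including "Occurrence of an RVP-001 related AE or SAE which results in death", and leave the judgement to the investigator. They do not say which 9.10.6 categories count as related.

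**The concern.** The scale reads as if written for repeated dosing, where treatment can be stopped or reduced and the event watched. Here each subject receives one intravenous bolus (Section 4.1) over about 5 to 15 seconds (Section 7.1.2). By the time an AE is seen there is no dose left to withdraw, so the dechallenge condition can only record whether the event goes away by itself.

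That makes persistence count against a drug-related rating. It also leaves the investigator without a clear instruction for an event that follows the injection, has no other explanation and does not resolve. Two careful investigators could rate the same event differently, one by the header and Table 7, the other by the exception. The rating feeds stopping rules in a first-in-human study, and also SUSAR status (Section 9.10.3) and subject replacement (Section 6.2).

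**Working it through.** **Plan figures.** The plan states no figure that depends on this scale, so there is none to reproduce. The sizes used below are 4 × 8 = 32 subjects and 4 × 6 = 24 on RVP-001 (Section 6.2).

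**Classification.** Each row sets the type of event against the mandatory conditions, for an event not clearly and solely extraneous.

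| Temporal link | Alternative cause | Resolves | Literal headers | Exception applied |
|---|---|---|---|---|
| Yes | No | Yes | Probable | Probable |
| Yes | No | No | None | Probable, if relatedness is already clear |
| Yes | Yes | Either | Possible | Possible |
| No | Yes | Either | Remote | Remote |

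The second row is the problem. It fails Probable on dechallenge, Possible on the alternative cause, Remote on the temporal link, and Unrelated because no extraneous cause is identified. Table 7 read as a strict grid also gives no category for it, whether or not the response pattern is known. (The Probable cell for temporal association is blank in the text available here; I took it as a plus and do not treat the blank as an error.)

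Comparing the second and third rows, an alternative explanation is evidence against the drug, yet it moves the persistent event from no category into Possible, which 9.10.1 counts as a reaction to the drug.

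**Rules that need relatedness.** One related SAE in a cohort (8.3.2); two related SAEs in a cohort, two subjects with severe related AEs, and a related death (8.3.3).

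**Rules that do not.** Any single SAE interrupts dosing and/or recruitment until the SRC has reviewed (8.3.3). Moderate or severe AEs in at least half of a cohort suspend dosing at that level or higher, as do the laboratory, vital-sign and ECG rules at three or more subjects (8.3.2).

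**Where the gap falls.** Half of a cohort of 8 is 4 subjects. Two subjects with severe but non-serious AEs are 2/8 = 25%, below that trigger, and no SAE rule applies to them. The rule left for that situation is the two-subject rule, which depends on the rating.

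**Illustration.** Let p be the true rate of severe drug-caused AEs and s the share rated related. Neither is in the documents; both are assumptions. With q = p × s and independent subjects, the chance of reaching two over 24 active subjects is 1 − (1 − q)^24 − 24q(1 − q)^23.

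| p | s = 1 | s = 0.75 | s = 0.5 |
|---|---|---|---|
| 5% | 0.339 | 0.227 | 0.120 |
| 10% | 0.708 | 0.546 | 0.339 |
| 20% | 0.967 | 0.894 | 0.708 |

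For example, at p = 10% and s = 0.5, q = 0.05 and 1 − 0.95^24 − 24 × 0.05 × 0.95^23 = 1 − 0.292 − 0.369 = 0.339. The severe-AE rule carries no cohort limit in its wording, hence 24. For a single cohort of 6 active subjects, the fall from s = 1 to s = 0.5 is 0.033 to 0.009, 0.114 to 0.033, and 0.345 to 0.114 at the three rates.

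**The case against.** The best defence is the exception in the dechallenge bullet. Its examples are illustrative, and if it is applied the persistent, unexplained event becomes Probable. A reader might infer that such events can never be rated related; the text does not support that. What survives is that the exception asks for clear relatedness before the scale has established it, which is hard to meet for a drug not previously given to humans. It also sits under a header saying the condition must apply, and is missing from Table 7.

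A reader might also infer that a fatal event could slip past the safety rules. It could not go unreviewed: every death is an SAE, any SAE interrupts dosing and/or recruitment regardless of cause, and SAEs go to the sponsor and the IRB within 24 hours (Section 9.10.7). Seizure, stroke, cerebral venous thrombosis and the QTc events are reported regardless of causality (Section 9.10.12). Only the related-SAE and related-death rules could be missed.

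Three further points for the defence hold:

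- Re-challenge and known pattern are not mandatory under the headers; only a strict reading of Table 7 makes them so. The Mn class concerns in Sections 4.3.3 and 9.10.12 may supply some known pattern.
- Crossing temporal link, alternative cause and resolution gives eight combinations, and a reader could count three as unclassified under the literal headers. Two of those have neither a temporal link nor another cause and owe nothing to dechallenge, so that count does not measure this problem.
- Damage to tables of related AEs cannot be claimed. The protocol describes no such tables and leaves AE summaries to a SAP (Section 10.2.3).

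The remaining exposure is also narrow. Grade 3 in Table 6 includes disabling events and those needing hospitalization, so many severe AEs would already be SAEs. The Data Safety Monitoring Plan and the safety plan, which are not available here, may add guidance.

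**Conclusion.** The point holds as an internal conflict in a stated rule, and the sponsor should correct it. On the literal headers and Table 7, a temporally linked, otherwise unexplained, persistent AE has no category, and an alternative explanation moves it into one that 9.10.1 treats as drug-related. Section 9.10.6 describes that same category as an unlikely link, so the two sections also disagree on what Possible means.

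The exposure is chiefly severe, non-serious AEs counted toward the two-subject rule, and secondarily the related-SAE and related-death rules. The documents give no basis for a numerical size. The probabilities above show only how sensitive the two-subject rule is to misrating, under assumed event rates and an assumed share missed. The conclusion assumes that related means Possible or Probable, which 9.10.1 suggests but Section 8.3 does not say.

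**What to change.** Reconcile the headers of Section 9.10.6, the exception and Table 7 so that every AE falls in exactly one category in a single-dose study:

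- Make dechallenge a supportive feature of Probable and not a condition.
- Show re-challenge and known pattern as supportive in Table 7, as the headers already imply.
- Align the description of Possible with Section 9.10.1.
- State in Section 8.3 which categories count as related to RVP-001.

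The stopping thresholds stay as they are. The cost is a text amendment to these sections, which needs IRB approval under Section 11.1.1, and a matching change to the eCRF completion guidance. The downside is that slightly more AEs may be rated related.
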